10. SUBJECT COMPLETION/WITHDRAWAL

10.1. Completion

A subject will be considered to have completed the study if he or she has completed all assessments of the Final Study Visit.

10.2. Discontinuation of Study Treatment

If a subject's study treatment must be discontinued before the end of the treatment regimen, this will not result in automatic withdrawal of the subject from the study.

A subject's study treatment should be discontinued if:

- The investigator believes that for safety reasons (eg, AE) it is in the best interest of the subject to discontinue study treatment
- The subject becomes pregnant
- The subject undergoes mechanical ventilation
- The subject requires peritoneal dialysis, hemodialysis, or hemofiltration
- The subject has an eGFR ≤ 30 mL/min/1.73 m² according to the MDRD equation
- The subject experiences any of the laboratory abnormalities as specified in Section [9.3.6](#), Specific Toxicities.

If a subject prematurely discontinues study treatment, follow-up assessments should be obtained and scheduled assessments should be continued. If a subject drops out due to withdrawal of consent, he or she will be offered an optional Safety Follow-up Visit.

10.3. Withdrawal From the Study

A subject will be withdrawn from the study for any of the following reasons:

- Lost to follow-up
- Withdrawal of consent
- Death

If a subject is lost to follow-up, every reasonable effort must be made by the study site personnel to contact the subject and determine the reason for discontinuation/withdrawal. The measures taken to follow up must be documented.

When a subject withdraws before completing the study, the reason for withdrawal is to be documented in the eCRF and in the source document. Study drug assigned to the withdrawn subject may not be assigned to another subject. Subjects who withdraw will not be replaced. If a subject withdraws from the study before the end of the treatment or the follow-up phase, he or she will be offered an optional Safety Follow-up Visit.

A subject who withdraws from the study will have the following options regarding the optional research sample:

- The collected sample will be retained and used in accordance with the subject's original separate ICF for optional research samples.
- The subject may withdraw consent for optional research sample, in which case the sample will be destroyed and no further testing will take place. To initiate the sample destruction process, the investigator must notify the sponsor study site contact of withdrawal of consent for the optional research samples and to request sample destruction. The sponsor study site contact will, in turn, contact the biomarker representative to execute sample destruction. If requested, the investigator will receive written confirmation from the sponsor that the sample has been destroyed.

Withdrawal From the Use of Samples in Future Research

The subject may withdraw consent for use of samples for research (see Section 16.2.5, Long-Term Retention of Samples for Additional Future Research). In such a case, samples will be destroyed after they are no longer needed for the clinical study. Details of the sample retention for research are presented in the main ICF.

11. STATISTICAL METHODS

Statistical analysis will be done by the sponsor or under the authority of the sponsor. A general description of the statistical methods to be used to analyze the efficacy and safety data is outlined below. Specific details will be provided in the Statistical Analysis Plan.

11.1. Subject Information

For all subjects who receive at least 1 dose of study drug descriptive statistics will be provided. All demographic characteristics (eg, age, race, height, body weight, body mass index [BMI]) and other initial subject characteristics (physical examination, medical and surgical history, concomitant diseases, etc.) will be tabulated and analyzed descriptively.

11.2. Sample Size Determination

Up to 90 subjects in total will be enrolled in this study. An effort will be made to include at least 24 subjects for each cohort, with the total of subjects allowed to be recruited across both cohorts.

It is anticipated that it is feasible to recruit at least 60 subjects, which would lead to an acceptable precision for the primary objective.

For the primary objective of evaluating the PK of JNJ-63623872 across age cohorts the PK parameters considered of major importance are C_{min} , C_{max} , and AUC_{12h} . As there are no data available where Day 3 has been part of extensive PK sampling on the 600 mg bid dose, the variability on days with available data are presented in [Table 2](#). Based on those data a between-subjects CV of 60% was assumed as a reasonably conservative estimate for the current study.

Table 2: Variability for Key Pharmacokinetic Parameters for JNJ-63623872 600 mg bid (Between-subjects %CV)

Time point	N	C_{min}	C_{max}	AUC_{12h}
Day 1	12	NA	65	56
Day 5	18	77	57	61
Day 5*	18	48	57	46
Day 10	12	56	44	43

[figure not shown]
Note: Based on study 63623872FLZ1001.

*JNJ-63623872 600 mg bid + oseltamivir 75 mg bid.

NA: Not applicable.

For age cohorts it was assumed that the number of hospitalizations would be about equal for elderly and non-elderly adults. In case 60 subjects are enrolled, there are 40 subjects on active treatment and it is assumed that at least 16 subjects are on active treatment in each cohort). For the comparison of PK parameters of the cohort of elderly adults (test) vs. non-elderly adults (reference) with PK data in a 16 to 24 ratio and a between-subject coefficient of variation (CV) of 60%, the 90% confidence interval (CI) of the geometric mean ratio (GMR) for C_{min} would be predicted to have a half-width of 35%, indicating that we can be 90% confident that the true GMR is in the interval observed GMR/1.35 to 1.35*GMR. If 90 subjects were enrolled with 60 on active treatment in a 24 to 36 ratio, the predicted half-width would be 28%.

The precision was expressed as the half-width of the 90% confidence band around the predicted mean LOESS estimate (illustrated in a simulated situation presented in [Figure 1](#), with circles as the individually simulated values for C_{min} , as a solid line the predicted values and the shaded area the 90% confidence band for the prediction). With the anticipated numbers of subjects, the average half-widths and the maximum half-width are presented in [Table 3](#) as percentages. The average half-width is the relative distance between the prediction and the 90% confidence band around that mean, averaged across the observed data points. Based on 40 to 60 subjects exposed to JNJ-63623872, the 90% confidence band for the planned LOESS regression was considered sufficiently precise (with average half-widths less than 25%) in order to evaluate the relationship between age and the major PK parameters.

Figure 1: Example of LOESS Regression for a Simulated Data Set for C_{min} (N=50)**Table 3: Precision of the LOESS Confidence Band Around the Prediction**

C_{min} (CV=60%)	Number of subjects treated with JNJ-63623872		
	N=40	N=50	N=60
Mean half-width*	25%	22%	20%
Maximum half-width*	46%	40%	36%

*Expressed as the ratio of the upper 90% confidence band divided by the prediction derived from the LOESS regression. Expressed as a percentage, based on 10,000 simulations.

For the safety objective of the study the sample size of 40 to 60 subjects treated with JNJ-63623872 can be characterized by assessing the precisions for (potentially) observed treatment-emergent AEs. For example, if no related treatment-emergent SAE is observed in a sample of 60 subjects exposed to JNJ-63623872, it can be concluded with 95% confidence that the true incidence of related treatment-emergent SAEs will be less than 5%. Table 4 presents the one-sided upper confidence limits for a range of numbers of treated subjects.

Table 4: Upper Confidence Limits for any Event with a Zero Incidence

	Number of subjects treated with JNJ-63623872		
	N=40	N=50	N=60
Upper confidence limit*	7.2%	5.8%	4.9%

*Upper 95% confidence limit (one-sided) using the Clopper-Pearson method

Besides characterizing the precision for excluding significant side-effects, the current study also allows to assess the incidence of treatment-emergent AEs on JNJ-63623872 vs. placebo treatment. Table 5 presents the 95% CIs for the risk difference that may potentially be observed.

For example, with 4 events (out of 60) vs. 1 event (out of 30) the risk difference (95% CI) would be 3.3% (-19%, 26%).

Table 5: Risk Differences and Associated 95% Confidence Intervals for Potential Treatment-emergent Adverse Event Incidences

Risk difference (95% CI) by sample size (active: placebo)		
40:20	50:25	60:30
0% (-28%, 28%)	0% (-25%, 25%)	0% (-22%, 22%)
2.5% (-25%, 30%)	2.0% (-23%, 27%)	1.7% (-21%, 24%)
5.0% (-23%, 32%)	4.0% (-21%, 28%)	3.3% (-19%, 26%)
7.5% (-20%, 35%)	6.0% (-19%, 30%)	5.0% (-18%, 27%)
10.0% (-18%, 37%)	8.0% (-17%, 32%)	6.7% (-16%, 29%)

Based on exact 95% confidence intervals. Interval width only depends on risk difference. For zero events in both groups the confidence interval for the risk difference is not defined.

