Nasal MT swabs collected will be used for sequence analysis of the polymerase basic protein 2 (PB2) region of the influenza virus polymerase and the neuraminidase gene at the time points specified in the [TIME AND EVENTS SCHEDULE](#). Exploratory sequencing of other regions of the influenza virus genome may also be performed.

Phenotyping

Nasal MT swabs will be used for analysis of phenotypic resistance against JNJ-63623872 and other antivirals at the time points specified in the [TIME AND EVENTS SCHEDULE](#).

BIOMARKER EVALUATIONS

Blood samples will be collected at the time points specified in the [TIME AND EVENTS SCHEDULE](#) for the exploration of blood biomarkers (eg, host ribonucleic acid [RNA], proteins including serum cytokines), on the premise that these markers may play a role in the blood concentrations, treatment response, or safety of JNJ-63623872 or oseltamivir, or the status and change of the influenza virus related disease. Where local regulations permit, an optional blood sample for exploratory host DNA research may also be collected.

In addition, nasal swabs collected for other testing may be used for biomarker analyses if available.

STATISTICAL METHODS

Since this is an exploratory study, no formal sample size calculation has been performed.

Up to 90 subjects in total will be enrolled in this study. An effort will be made to include at least 24 subjects for each cohort, with the total of subjects allowed to be recruited across both cohorts. It is anticipated that it is feasible to recruit at least 60 subjects, which would lead to an acceptable precision for the primary objective.

For age cohorts it was assumed that the number of hospitalizations would be about equal for elderly and non-elderly adults. In case 60 subjects are enrolled, there are 40 subjects on active treatment and it is assumed that at least 16 subjects are on active treatment in each cohort. For the comparison of PK

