parameters of the cohort of elderly adults (test) vs. non-elderly adults (reference) with PK data in a 16 to 24 ratio and a between-subject coefficient of variation (CV) of 60%, the 90% confidence interval (CI) of the geometric mean ratio (GMR) for minimum plasma concentration (C_{\min}) would be predicted to have a half-width of 35%, indicating that we can be 90% confident that the true GMR is in the interval observed GMR/1.35 to 1.35*GMR. If 90 subjects were enrolled with 60 on active treatment in a 24 to 36 ratio, the predicted half-width would be 28%.

For the safety objective of the study, the sample size of 40 to 60 subjects treated with JNJ-63623872 can be characterized by assessing the precisions for (potentially) observed treatment-emergent AEs. For example, if no related treatment-emergent serious adverse event (SAE) is observed in a sample of 60 subjects exposed to JNJ-63623872, it can be concluded with 95% confidence that the true incidence of related treatment-emergent SAEs will be less than 5%.

The primary PK analysis will be done on the PK-evaluable population, defined as all subjects who received active study treatment (JNJ-63623872 and oseltamivir), with evaluable PK measurements on Day 3.

Descriptive statistics will be used for all endpoints and will be tabulated by treatment arm and age cohort. No formal statistical hypothesis testing will be performed. Subgroup analyses may be summarized descriptively using baseline characteristics.

Primary Endpoint

- PK parameters of JNJ-63623872 (ie, C_{\min} , C_{\max} , and AUC_{12h}) established on Day 3.

Secondary Endpoints

1. The proportion of subjects experiencing AEs, SAEs, and treatment-emergent grade 1-4 laboratory abnormalities.
2. Time to return to usual activity and usual health (Questions 5 and 9 of the additional items for the Flu-PRO).
3. Time to significant reduction in influenza symptom severity.
4. Proportion of subjects with a significant reduction (to mild or none for all influenza symptoms) at each assessment.
5. Disease status and incidence of complications associated with influenza after the start of study treatment, and disease progression:
 - bacterial pneumonia (culture confirmed where possible),
 - other bacterial superinfections,
 - respiratory failure,
 - pulmonary disease (eg, COPD),
 - cardiovascular and cerebrovascular disease (eg, myocardial infarction, CHF, arrhythmia, stroke).
6. Duration and severity of clinical symptoms as measured by the Flu-PRO.

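### The precision stated for the primary PK comparison at 60 and 90 enrolled counts every active subject as PK-evaluable on Day 3 (minor; a missing allowance, not an arithmetic error)

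*Protocol*

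**What the plan says.** Protocol 11.2 starts from enrolment: "In case 60 subjects are enrolled, there are 40 subjects on active treatment". It then compares elderly with non-elderly adults "with PK data in a 16 to 24 ratio and a between-subject coefficient of variation (CV) of 60" per cent and predicts a half-width of 35% for Cmin. For the upper end of enrolment: "If 90 subjects were enrolled with 60 on active treatment in a 24 to 36 ratio, the predicted half-width would be 28" per cent. Recruiting at least 60 subjects is judged feasible, "which would lead to an acceptable precision for the primary objective". The Synopsis repeats the GMR figures, and SAP 1.4 repeats the whole calculation.

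Protocol Table 3 (SAP Table 2) gives the precision of the LOESS band for N = 40, 50 and 60 under the column heading "Number of subjects treated with JNJ-63623872".

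The Synopsis (Statistical Methods) defines the population for the primary PK analysis as "all subjects who received active study treatment (JNJ-63623872 and oseltamivir), with evaluable PK measurements on Day 3". Several passages say who will have no Day 3 profile, and they differ. The Synopsis and Protocol 3.1, 6 and 9.2.1 exempt subjects discharged earlier than Day 3. Footnote t of the in-hospital Time and Events Schedule also exempts those discharged on Day 3 itself.

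The Synopsis adds: "Since this is an exploratory study, no formal sample size calculation has been performed".

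**The concern.** The chain runs from enrolled to active to subjects in the PK comparison, and the last step loses nobody: 16 + 24 = 40 and 24 + 36 = 60. The protocol itself expects losses at that step. Early discharge removes the Day 3 profile, Protocol 10.2 lists reasons to stop treatment, Protocol 10.3 does not replace withdrawals, and Protocol 11.3 has a rule for a cohort in which most subjects lack a reliable AUC12h. No evaluability rate, inflation or sensitivity range is given.

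With no formal sample size calculation, precision for the primary objective is the reason given for regarding 60 enrolled as acceptable. A reader is likely to take 35% as what 60 enrolled will deliver and 28% as what 90 will deliver. If some active subjects have no evaluable Day 3 PK, the intervals will be wider than that.

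**Working it through.** **Inputs.** Two-sided 90% interval (Protocol 11.3); between-subject CV 60%, 2:1 randomisation, cohort splits 16:24 and 24:36, and enrolment cap 90 (Protocol 5 and 11.2). The documents give no non-evaluable rate. I assume 10, 20 and 30%, equal in both cohorts.

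**Formula.** Half-width = exp( t(0.95, n1+n2−2) × s × sqrt(1/n1 + 1/n2) ) − 1, with s = sqrt(ln(1 + CV²)) = sqrt(ln 1.36) = 0.5545.

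**The plan's figures.**
- 16:24: exp(1.686 × 0.5545 × 0.3227) − 1 = 35.2% (stated 35%).
- 24:36: exp(1.672 × 0.5545 × 0.2635) − 1 = 27.7% (stated 28%).

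Both reproduce, with all 40 or all 60 active subjects evaluable.

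**With loss, same 2:3 cohort ratio, whole subjects.**

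| Assumed loss | 60 enrolled | 90 enrolled |
|---|---|---|
| none | 16:24, 35.2% | 24:36, 27.7% |
| 10% | 14:22, 37.8% | 22:32, 29.3% |
| 20% | 13:19, 40.3% | 19:29, 31.6% |
| 30% | 11:17, 44.2% | 17:25, 34.1% |

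The protocol expects about equal hospitalisation numbers in the two age groups. Equal cohorts help a little: 36.7, 39.5 and 43.0% at 60 enrolled, and 28.8, 30.8 and 33.4% at 90.

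**How much loss the stated figures absorb, to the nearest per cent.**
- 60 enrolled: from 16:24, one loss gives 16:23 = 35.6%, which rounds to 36%. Equal cohorts absorb two losses (19:19 = 35.49%).
- 90 enrolled: three of 60 lost (5%) gives 23:34 = 28.46%, still 28%.

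**Room under the cap.** At 90 enrolled there are 60 active subjects, and losing one third leaves 40. Enrolment that keeps 40 evaluable is 1.5 × 40/(1 − loss), with active subjects and then enrolment rounded up: 68, 75 and 87 at 10, 20 and 30% loss.

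**Sensitivity to the CV (Cmin, Protocol Table 2).** At 16:24 with no loss, CV 48% (the combination arm) gives 28.1% and CV 77% gives 45.0%. At CV 48%, s = 0.4553; 20% loss (13:19) gives 32.1%, and 30% loss (11:17) gives exp(1.706 × 0.4553 × 0.3870) − 1 = 35.1%.

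**LOESS band.** The smoothing settings are not given, so this only scales Table 3 by 1/sqrt(N) on the log scale. At 20% loss, 60 enrolled leaves 32 evaluable, below the table's smallest column: exp(ln 1.25 × sqrt(40/32)) − 1 = 28.3%, against 25% tabulated at 40. At 90 enrolled, 48 evaluable gives exp(ln 1.20 × sqrt(60/48)) − 1 = 22.6%, against 20% at 60.

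**The case against.** The strongest defence is that the calculation is already conditional. The 35% sentence refers to subjects with PK data, and for 40 such subjects it is right. This stands, so a reader who infers an arithmetic error goes too far. It does not remove the gap, because the same paragraph reaches those 40 from 60 enrolled, and the sentence on 90 enrolled refers only to subjects on active treatment.

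The 60-to-90 range also gives room. That holds for 35%, although the documents do not present the range as an allowance. It does not hold for 28%, which sits at the cap.

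The loss rate is my assumption, and the CV matters more. Both stand. The combination arm is the regimen studied here, and at its Cmin CV of 48% the 35% survives even a 30% loss. At 77% the precision is worse than stated with no loss at all.

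Finally, the study is exploratory, no hypothesis is tested (Protocol 2.2), and no numeric threshold defines acceptable GMR precision. This also stands, so a reader should not infer that the trial is undersized or that a decision rule fails. SAP 1 leaves the detailed PK analysis to a Clinical Pharmacology Analysis Plan, which was not available. It may deal with evaluability, but the statements at issue are in the protocol and SAP.

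A reader might also see a contradiction in the LOESS text, "considered sufficiently precise (with average half-widths less than 25" per cent), beside a tabulated 25% at N = 40. Table 3 shows whole per cents, so a value just under 25% would print the same. Rounding can explain it, and I do not count it as an error.

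**Conclusion.** The point holds as a minor gap in a precision statement. The half-widths of 35% and 28% are correct for 40 and 60 PK-evaluable subjects, but they are presented as following from 60 and 90 enrolled with no allowance for active subjects without evaluable Day 3 PK. For an assumed loss of 20%, equal across cohorts and at CV 60%, they become about 40% and 32%. The 28% figure tolerates only about 5% loss. These sizes depend on the assumed loss rate and CV. The missing allowance itself does not.

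The two versions of the early-discharge rule are a real mismatch, because they determine who can enter the primary population.

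One further inference from the same section is not supported: that the 0% row of Protocol Table 5 (SAP Table 4) contradicts its footnote on zero events in both groups. That row fits 2 active events against 1 placebo event (2/60 − 1/30 = 0), so it need not describe zero events.

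**What to change.** In Protocol 11.2, the Synopsis and SAP 1.4, give the GMR half-widths by number of subjects PK-evaluable on Day 3, and relabel the columns of Protocol Table 3 (SAP Table 2) in the same way. State an assumed non-evaluable rate with its basis, and restate the half-widths at 60 and 90 enrolled under it (for example, about 40% and 32% at 20%).

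Reconcile the Synopsis and Protocol 3.1, 6 and 9.2.1 with footnote t of the Time and Events Schedule on whether discharge on Day 3 itself rules out intensive sampling.

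The cost is a few text and label edits. The enrolment cap and the analyses do not change. The downside is that the stated precision becomes slightly less favourable.

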11.3. Pharmacokinetic Analyses

Pharmacokinetic parameters will be used to assess the exposure of JNJ-63623872 on Day 3. Refer to Section 9.2 for more details.

Primary Endpoint

- PK parameters of JNJ-63623872 (ie, C_{min} , C_{max} , and AUC_{12h}) established on Day 3.

Intensive Pharmacokinetic Sampling (Day 3)

All plasma concentrations below the lowest quantifiable concentration or missing data will be labeled as such in the concentration data presentations or SAS dataset. Concentrations below the lower quantifiable concentration will be treated as zero in the summary statistics. All subjects and samples excluded from the analysis will be clearly documented in the Clinical Study Report.

Descriptive statistics will be calculated for plasma concentrations of JNJ-63623872 at each sampling time point and for the derived plasma PK parameters. Statistics include sample size (n), mean, standard deviation (SD), %CV, geometric mean, median, minimum, and maximum.

For each subject treated with JNJ-63623872, JNJ-63623872 plasma concentration-time data will be graphically presented. Similarly, graphs of the mean plasma concentration-time profiles and overlay graphs with combined individual plasma concentration-time profiles will be produced. Pharmacokinetic parameters will be subjected to an exploratory graphical analysis in order to get a general overview.

Statistical analysis will be performed for the PK-evaluable population. Elderly adults (65 to ≤ 85 years) will be compared vs. non-elderly adults (reference) to investigate the relative effect of age. The primary PK parameters are C_{max} , C_{min} , and AUC_{12h} . AUC_{12h} will be rejected as primary parameter for an age cohort if more than half of the subjects of that age cohort do not have a reliable value. For the primary PK parameters, the GMR of test vs. reference will be calculated including the associated 90% CI.

For the assessment of an age effect, regression techniques will be employed to describe and predict the relation between age and primary PK parameters. As the relationship need not be linear across age, LOESS regression will be used that allows for a nonlinear model fit. The LOESS model uses smoothing based on goodness of fit criteria; recognizing that marked local changes are not biologically plausible, smoothing will be restricted. In case important predictive covariates are identified a generalized additive model will be used to model the relation between age and PK parameters adjusted for covariates, including LOESS regression for age. Regression will be performed on the logarithm of the PK parameter, with the results of the regression being retransformed to the original scale, including the 90% confidence band around the regression line. For an effect of body weight on primary PK parameters a similar approach will be used as an exploratory analysis.

Special attention will be paid to the plasma concentrations and PK parameters of those subjects who have discontinued the study for an AE, or who experienced an AE of at least grade 3, or an SAE.

Sparse Pharmacokinetic Sampling

Population PK analysis of plasma concentration-time data of JNJ-63623872 will be performed using nonlinear mixed-effects modeling. Data may be combined with those of other selected studies to support a relevant structural model. Available baseline subject characteristics (demographics, body weight, laboratory variables, genotypes, race, etc.) will be tested as potential covariates affecting PK parameters. Details will be given in a population PK analysis plan and the results of the population PK analysis will be presented in a separate report.

A snapshot date for PK samples to be analyzed will be defined, if required. Samples collected before this date will be analyzed for JNJ-63623872 and included in the population PK analysis. Samples collected after the snapshot date will be analyzed at a later date, and may be included in a population PK re-analysis when they become available after database lock.

Data will be listed for all subjects with available plasma concentrations per treatment arm. Subjects will be excluded from the PK analysis if their data do not allow for accurate assessment of the PK (eg, incomplete administration of the study drug; missing information of dosing and sampling times; concentration data not sufficient for PK parameter calculation).

All concentrations below the lowest quantifiable concentration or missing data will be labeled as such in the concentration database. All subjects and samples excluded from the analysis will be clearly documented in the study report.

For each treatment arm, descriptive statistics, including sample size (n), arithmetic mean, SD, %CV, geometric mean, median, minimum, and maximum will be calculated for all individually derived PK parameters including exposure information of JNJ-63623872.

